will include only DCIS patients who have available claims data (i.e. are enrolled in fee-for-service coverage) during the period between cancer diagnosis and the end of the follow-up (Aim 1: 9 months after DCIS diagnosis; Aim 2: either death or the last date of claims released by SEER-Medicare). Statistically, we plan to create an “unknown” category to capture those patients who had a missing value. Additionally, we will conduct sensitivity analyses regarding whether or not excluding these patients would change our findings.

To compare baseline characteristics between intervention and control groups, we will conduct standard descriptive statistics using χ^2 tests for categorical variables and t-tests for continuous variables. We will tabulate the frequencies of outcomes of interests by the intervention vs. control group. We will use multivariable analyses to test our hypotheses while controlling for unbalanced covariates, as described below.

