We plan to control for selection bias using propensity score matching methodology.¹⁷ Specifically, the propensity score matching will be based on the Mahalanobis distance¹⁸ calculated using age, race, residence in a metropolitan county, comorbidity, prior influenza vaccination or prior visit to a primary care physician (both as proxies for access to care), income, preoperative MRI use, and tumor characteristics. Tumor characteristics include size, grade, comedonecrosis, and estrogen receptor status. By incorporating these factors in matching, we expect to substantially decrease bias and balance the risk for outcomes of interest between the SLNB and non-SLNB groups. We will use 2: 1 matching, as prior literature indicated that this approach results in improved precision without a commensurate increase in bias.¹⁹ To ensure robust and comprehensive matching, matches will be assigned by choosing the two best non-SLNB patient matches for each SLNB patient; when two or more SLNB patients match the same control (that is, have Mahalanobis distances minimized by the same control), one will be randomly selected as a match, and this process reiterates until all SLNB patients have two matched controls. We will assess the validity of the matching by comparing risk factors between the SLNB and non-SLNB groups using χ^2 tests. The difference in outcomes between the control and intervention groups will be estimated in a Kaplan-Meier curve. We will estimate the relative risk in the propensity score matched sample using the standard method for matched-pair data.²⁰ We will use the Cox proportional hazards models to investigate the association between various factors (grade, tumor size, and estrogen receptor status) and outcomes.²¹

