For multivariable analyses, we will use conditional logistic regression models for acute/subacute side effects (primary outcomes) and treatment received (mastectomy or radiation therapy; secondary outcomes) in Aim 1, with conditioning on the matched variable. For primary outcomes, we will run 2 models, with or without controlling for treatment received. We will report adjusted odds ratios of SLNB on these outcomes. In Aim 2, we will apply time-to-event models to test whether the intervention is associated with better outcomes, including primary and secondary outcomes. We will report adjusted hazard ratios of SLNB on these outcomes. The proportional hazards assumption will be evaluated for each model using a variety of methods (evaluation of Kaplan-Meier and log(-log) survival plots, Schoenfield residuals, and covariate x time interactions). If the proportional hazards assumption is violated, we will instead use parametric survival models, using AIC and BIC to determine the best parameterization (exponential, Weibull, generalized gamma, Gompertz, lognormal, or loglog). All time-to-event models will incorporate a shared frailty term for the matching group, and will include covariates that are not balanced by matching. These models will allow us to test for association between various factors (grade, tumor size, and estrogen receptor status) and outcomes.

In order to identify suitable patient subgroups that may be able to forego SLNB, we plan to explore the following stratification schemes in Aim 2 analysis: 1. Stratify patients by receipt of radiation therapy; 2. Stratify patients by key DCIS characteristics, including grade, comedonecrosis and tumor size; 3. Stratify patients by their predicted life expectancy, given their age, sex and comorbidities.

Expected outcomes of the study

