According to our specific aims, we propose different outcomes of interest. For Aim 1, our primary outcome is the side effect occurrence within 9 months post-DCIS-diagnosis. The side effects include lymphedema, pain and limitation of movement of extremities. Our secondary outcome for Aim 1 is treatment received. We will examine the relationship between SLNB and subsequent treatment received, including mastectomy within 6 months after DCIS diagnosis and radiation therapy within 9 months after DCIS diagnosis. For Aim 2, we propose several primary outcomes. We will measure the breast cancer specific survival with the timeframe from 9 months post-diagnosis to death or end of study period. We will also assess the ipsilateral invasive breast cancer occurrence and treated recurrence, including mastectomy, within the same timeframe. For Aim 2, our secondary outcomes include overall survival (a benchmark outcome to check the performance of analytic models) and lasting side effects.

As for detailed outcome measurements, we expect to have these estimates by the end of the project: 1. the difference in baseline characteristics between the intervention and control groups and χ^2 statistics that suggests difference significance; 2. the propensity score matching results, including matched cohort and the standardized difference that indicates the balance of matching; 3. the estimate in the main analysis, for example odds ratio, rate ratio or hazard ratio, that could represent the association of intervention and outcome; 4. the estimate in the stratified analysis that could describe the association of intervention and outcome in each clinical subgroup.

Duration of the project

We are anticipating the project to be completed within 18 months of time.

Ethical concerns

As a result of the nature of our observational design, we do not anticipate any ethical concerns as we are analyzing existing data. We expect this project will be exempt from full review. However, we will make sure that no member in the project would violate the rules and confidentiality required when analyzing SEER-Medicare database.

References

2. American Cancer Society. Cancer Facts & Figure 2013. Atlanta: American Cancer Soc; 2013

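### The adjustment set and the balance criterion are not fixed: one section lists covariates unconditionally, another ties adjustment to imbalance, and two balance measures are named without a threshold or a trigger

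*Combined protocol and SAP*

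**What the plan says.** Five places in the combined protocol and SAP bear on this.

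- **Methodology, last paragraph.** A list of covariates to control confounding: demographics including year of diagnosis, socioeconomic factors, comorbidity, DCIS characteristics (grade, size, comedonecrosis, hormone receptor status), utilization, and treatment received. No balance condition is attached.
- **Data management and statistical analysis, paragraph on descriptive comparisons.** "We will use multivariable analyses to test our hypotheses while controlling for unbalanced covariates, as described below".
- **Same section, matching paragraph.** The tumor variables used in matching are defined: "Tumor characteristics include size, grade, comedonecrosis, and estrogen receptor status". The check is: "We will assess the validity of the matching by comparing risk factors between the SLNB and non-SLNB groups using χ^2 tests". The paragraph closes with Cox models for grade, size and estrogen receptor status, again with no balance condition.
- **Same section, multivariable paragraph.** All time-to-event models carry a shared frailty term for the matching group and "will include covariates that are not balanced by matching". The next sentence reads: "These models will allow us to test for association between various factors (grade, tumor size, and estrogen receptor status) and outcomes".
- **Expected outcomes of the study.** The matching results are to include "the standardized difference that indicates the balance of matching".

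No alpha, balance threshold, sample size or event count appears in the text supplied.

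**The concern.** Two analysts could both follow this plan and fit different models. One enters the Methodology list in full. The other enters only what fails a balance check, and must then choose between chi-square and standardized difference and pick a cut-off. Several listed covariates are not in the matching list (year of diagnosis, marital status, education, disability index, prior hospitalization, surgeon's volume), so for these the choice of reading matters most.

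The check named in the methods is a significance test. For a given imbalance its result changes with sample size alone: it tends to pass real imbalance in small samples and flag trivial imbalance in large ones. If it drives adjustment, confounder control depends on how many women are matched rather than on how different the groups are.

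The rule also sits badly with the sentence after it. Grade, size and estrogen receptor status are matching variables. The better the matching works, the less reason the rule gives for entering them in the models that are meant to test them.

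**Working it through.** The plan gives no figure to reproduce, so the arithmetic is illustrative. The 2:1 ratio is from the plan. The two-sided alpha of 0.05, the prevalences, the numbers of SLNB women and the relative risks are assumptions.

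**1. Size of the example imbalance.** For a binary covariate at 47.5% (SLNB) and 40% (no SLNB), the standardized difference is

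(0.475 − 0.40) / √[(0.475×0.525 + 0.40×0.60)/2] = 0.075 / 0.495 = 0.15.

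**2. Chance that chi-square flags it.** With n SLNB women and 2n controls, the pooled proportion is (0.475 + 2×0.40)/3 = 0.425. Then

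- SE₀ = √[0.425×0.575×(1/n + 1/(2n))]
- SE₁ = √[0.475×0.525/n + 0.40×0.60/(2n)]
- power = Φ[(0.075 − 1.96×SE₀)/SE₁]

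| SLNB women | SE₀ | SE₁ | Probability flagged |
|---|---|---|---|
| 100 | 0.0605 | 0.0608 | Φ(−0.72) = 0.24 |
| 300 | 0.0350 | 0.0351 | Φ(0.18) = 0.57 |
| 1,000 | 0.0191 | 0.0192 | Φ(1.95) = 0.97 |

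At the other end, 43% vs 40% (standardized difference 0.06) with 3,000 SLNB women is flagged with probability 0.78.

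**3. The same observed imbalance at different sizes.** An observed 55% vs 50% (standardized difference 0.10) gives p = 0.41 with 100 SLNB women and 200 controls, p = 0.068 with 500 and 1,000, and p = 0.0098 with 1,000 and 2,000. The standardized difference is the same each time.

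**4. What a missed factor costs.** For a factor with relative risk RR, the confounding ratio is [1 + 0.475(RR − 1)] / [1 + 0.40(RR − 1)].

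- RR = 2: 1.475/1.40 = 1.054, about 5%
- RR = 3: 1.95/1.80 = 1.083, about 8%

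**5. Can a balanced factor be estimated?** Yes. In a simulation of 700 matched 2:1 sets with an assumed grade hazard ratio of 2.0, set-level frailty in the data and a plain Cox fit, the grade effect came back at 1.94 (imperfect matching on grade) and 1.96 (exact matching). In the imperfectly matched case, the SLNB hazard ratio was 0.714 with grade entered and 0.716 without it. This covers a factor that really was balanced; it says nothing about imbalance that a test misses.

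**6. Chance imbalance under a 0.1 limit.** With perfect underlying balance, the standardized difference has standard error of about √(1/n + 1/(2n)). At n = 100 this is 0.122, so |d| > 0.1 occurs with probability 2×[1 − Φ(0.1/0.122)] = 0.41. At n = 1,000 the standard error is 0.0387 and the probability is 0.01. A 0.1 limit is therefore reasonable for a large matched cohort but a poor selection rule inside small strata.

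**The case against.** The plan can be defended on four counts.

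- **It does not say that only unbalanced covariates enter.** A reader might infer this, but the sentence is one of inclusion, and the Methodology list has no balance condition. This stands, and it makes the problem a conflict between sections rather than proof that prognostic factors are dropped. It does not remove the conflict, because the descriptive-comparison paragraph also ties control of confounding to imbalance.
- **Chi-square is not shown to be the trigger.** It is given as a check of the matching, and the standardized difference is already a planned output. This stands. The plan leaves the trigger undefined, with the sample-size-dependent measure as the only one named in the methods.
- **A reader might conclude that grade, size and receptor status cannot be tested.** The documents do not support that. The matching paragraph plans Cox models for these factors with no balance condition, and a balanced factor is estimable once entered. What remains is that the inclusion rule does not itself put them in the models.
- **A reader might turn the flagging probabilities into omission rates for the planned subgroups.** That would assume stratum sizes, an alpha and covariate reselection in every stratum, none of which the plan states. If covariates are chosen once in a full cohort of, say, 1,000 SLNB women, the example imbalance is flagged 97% of the time.

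Over-flagging in a large cohort is also a minor harm, since it mostly adds a covariate that was not needed.

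**Conclusion.** The point holds as a failure to fix the adjustment set and the balance criterion, together with a mismatch between the inclusion rule and the factor analyses promised from the same models. The quoted inclusion rule covers the Aim 2 time-to-event models; for Aim 1 the dependence on imbalance rests on the general sentence about multivariable analyses.

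Its likely size is modest. Under the stated assumptions, one missed factor at a standardized difference of 0.15 moves the SLNB ratio by about 5 to 8%, and leaving out a factor that is truly balanced hardly moves it. The main cost is an adjusted estimate whose model is settled after the data are seen, by a criterion that may depend on sample size. The change is worth making because it costs almost nothing.

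**What to change.** 1. **Fix the covariates.** In the descriptive-comparison and multivariable paragraphs, replace the reference to covariates unbalanced after matching with one adjustment set drawn from the baseline variables in the Methodology list: age, year of diagnosis, comorbidity, grade, size, comedonecrosis and receptor status. Enter it in the outcome models whatever the balance result. Grade, size and receptor status are then always in the Aim 2 models, as the factor analyses require. The planned Aim 1 models with and without treatment received are unaffected.
2. **Fix the balance criterion.** In the matching paragraph, replace chi-square with the standardized difference already listed in the expected outputs, and state a threshold for the full matched cohort (0.1 is an example; the documents give none).
3. **Strata.** Report standardized differences within strata descriptively, without reselecting covariates, because chance alone often exceeds 0.1 in small strata.

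The cost is wording: the covariates are already planned and the standardized difference is already an output. The downside is a few more model parameters. Where events are few, use a smaller pre-specified set or adjust for the propensity score, and say in advance when that applies.

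### The plan seeks subgroups that may forego SLNB from separate stratum estimates, with no SLNB-by-subgroup interaction and no interval criterion, so a small stratum's non-significant result could be read as no benefit

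*Combined protocol and SAP*

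**What the plan says.** The final paragraph of Data management and statistical analysis gives the purpose of the subgroup work, "In order to identify suitable patient subgroups that may be able to forego SLNB", and its status: "we plan to explore the following stratification schemes in Aim 2 analysis". Three schemes follow:

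- "Stratify patients by receipt of radiation therapy"
- "Stratify patients by key DCIS characteristics, including grade, comedonecrosis and tumor size"
- "Stratify patients by their predicted life expectancy, given their age, sex and comorbidities"

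The Aim 2 time-to-event models are there to "test whether the intervention is associated with better outcomes, including primary and secondary outcomes", and the reported measure is set by "We will report adjusted hazard ratios of SLNB on these outcomes". Expected outcomes of the study lists the subgroup product as "the estimate in the stratified analysis that could describe the association of intervention and outcome in each clinical subgroup".

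The only interactions named are covariate-by-time terms, which serve the proportional hazards check. The models involving grade, tumor size and estrogen receptor status examine how those factors relate to outcome, not whether they change the effect of SLNB. The plan gives no equivalence or non-inferiority margin, no minimum event count per stratum, no cut-points for size or life expectancy, and no rule for moving from a stratum estimate to a statement that SLNB can be omitted.

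**The concern.** To say that a subgroup may forego SLNB is to claim that any benefit there is absent or too small to matter. A test for benefit within the stratum cannot establish that. It can fail because there is no benefit or because there are few events, and the plan offers nothing to tell these apart.

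Comparing strata has the same weakness. A significant result in one stratum beside a non-significant result in another does not show that the effects differ. The difference has to be estimated directly, and the plan does not do so.

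What is at stake is a stated Aim 2 goal. A subgroup could be described as able to omit the procedure because it was small. Another could be described as benefiting because of a chance difference.

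**Working it through.** **No figure to reproduce.** The plan states no sample size, event count, alpha, power or target hazard ratio. What follows is illustration.

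**Inputs.** From the plan: two non-SLNB patients matched to each SLNB patient, so the SLNB share is 1/3. Assumed: two-sided 0.05; 20 to 100 events per stratum; true hazard ratios of 0.67 and 0.50 (0.7 in the second step); no allowance for clustering within matched sets.

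**1. Chance that a real benefit is missed in one stratum.**

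SE(log HR) = 1/√(d × 1/3 × 2/3), with d the number of events. Power is approximately Φ(|ln HR|/SE − 1.96), and the 95% interval multiplies and divides the estimate by exp(1.96 × SE).

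Example: for d = 20, SE = 1/√4.444 = 0.474. With HR 0.67, |ln HR|/SE = 0.400/0.474 = 0.84, so power is about 0.13.

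| Events in stratum | SE | Non-significant, true HR 0.67 | Non-significant, true HR 0.50 | Interval factor |
|---|---|---|---|---|
| 20 | 0.474 | 0.87 | 0.69 | 2.53 |
| 40 | 0.335 | 0.78 | 0.46 | 1.93 |
| 60 | 0.274 | 0.69 | 0.28 | 1.71 |
| 100 | 0.212 | 0.53 | 0.10 | 1.52 |

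A stratum with 20 events and an estimate of 1.0 would have a 95% interval of about 0.40 to 2.53, which still contains a halving of the hazard.

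**2. Apparent differences between strata with the same true effect.** Take a true HR of 0.7 in both strata and 400 events split 80/20. By the same formula, power is 0.853 with 320 events and 0.324 with 80. The large stratum is significant and the small one is not with probability 0.853 × (1 − 0.324) = 0.58, although nothing differs between them.

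**3. Events needed to exclude a benefit.** With true HR 1 and 80% power, using the 95% interval, d = (1.96 + 0.842)² / (2/9 × (ln M)²), where M is the hazard ratio of no SLNB to SLNB to be excluded. For M = 1.5 (SLNB hazard ratio 0.67) this is 7.85/(0.2222 × 0.1644) = 215 events. For M = 2.0 (hazard ratio 0.50) it is 74. These values of M are illustrations, not proposed margins.

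**4. Limits of an interaction test.** For 80% power, D = 7.85 / (2/9 × f(1 − f) × (ln RHR)²), with f the smaller stratum's share of events and RHR the ratio of hazard ratios. RHR 0.5 needs 295 events in total with an even split and 460 with a 20/80 split; RHR 0.7 needs 1,111 and 1,736. The test is itself weak, and it does not show absence of benefit within a stratum.

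**The case against.** The strongest defence is that the plan calls this work exploratory, names every stratifier in advance and promises estimates, not verdicts. Methodology also gives a prior reason for the radiation split: little benefit of SLNB is expected when radiation is given. These points stand. They make this something other than an unrestricted search, and the main Aim 2 estimates are unaffected. They do not supply a way to get from a stratum estimate to the stated purpose, and Methodology expects the result in patients without radiation to matter clinically.

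Four stronger readings are tempting, and the documents do not support them:

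- A reader might infer that the plan commits itself to treating a non-significant stratum as showing no benefit. No section says so. The gap is that no rule is written, which leaves that reading open.
- A reader might infer that the outcomes are rare and that most strata will be underpowered. The documents give no event rates, and one primary outcome is follow-up mastectomy, whose frequency is not stated. With 100 events and a true HR of 0.50, a miss has probability only 0.10.
- A reader might attach a family-wise false-positive rate. The number of strata is unknown without cut-points, the stratifiers re-divide the same patients, the outcomes are related, and a two-sided error counts false harm as well as false benefit. No such figure is defensible here.
- A reader might infer that an interaction test alone would settle the matter. It would not, for the reasons in step 4 of the working.

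**Conclusion.** The point holds as a mismatch between method and purpose: estimating SLNB's effect stratum by stratum, with a test for benefit only, cannot by itself support a statement that a subgroup may forego the procedure. It is more than a missing detail, because a better method is available from the same data.

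The absence of an interaction test and of an interval criterion is a matter of text and needs no assumption. The probabilities rest entirely on the assumed event counts, hazard ratios and significance level. Clustering within matched sets would alter them somewhat. The change should be made before the stratified analyses are run; it does not call the main Aim 2 analysis into question.

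**What to change.** In the stratification paragraph of Data management and statistical analysis:

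1. For the baseline stratifiers (grade, comedonecrosis, tumor size, predicted life expectancy), fit SLNB-by-stratifier interaction terms in the full matched cohort. Report the ratio of hazard ratios with its 95% interval. Define the cut-points in advance.
2. For each stratum, report the event count and 95% intervals for the hazard ratio and for the absolute risk difference at a fixed time.
3. State that any description of a subgroup as able to forego SLNB depends on whether the interval excludes a benefit size fixed in advance, and not on a non-significant p-value or on the interaction test alone. The study team must choose that size.
4. Present the radiation split with the same intervals, but flag it separately. Radiation is not among the matching variables, and the plan itself examines it in Aim 1 as a possible consequence of SLNB, so this split conditions on an unmatched, post-exposure variable.
5. Label the subgroup results hypothesis-generating.

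The cost is a few extra model terms and some wording, with no new data. Conclusions for small strata will be more cautious, and some strata may support no statement either way.

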Even when DCIS patients opt to receive a less intensive treatment such as BCS without radiation therapy, they and their providers need to decide whether to undergo sentinel lymph node biopsy (SLNB). The role of SLNB for DCIS management is controversial in general and needs further scrutiny in particular if patients received BCS without radiation therapy. Significant debates continue about whether SLNB should be performed,⁶⁻⁸ with some experts advocating for its use.^{9,10} Proponents of SLNB cite concerns that occult microinvasive disease within the DCIS may not be detected histologically, with an estimated prevalence of 1.4% to 12%.¹¹ However, among DCIS patients who receive radiation therapy the likelihood of local recurrence with axillary involvement is low,¹² and routine SLNB is not recommended.¹³ Of note, radiation therapy has also been shown to control micrometastasis if present.¹⁴ On the other hand, if we plan to empower DCIS patients to choose less intensive management options, such as BCS without radiation therapy, understanding the role of SLNB will be crucial.

A systematic literature review has shown that evidence gaps exist regarding the benefits of SLNB for DCIS.¹⁵ As far as we know, no study has yet examined SLNB among DCIS patients who received BCS. Because of the current call for less intensive treatment, it is imperative to understand the benefits or harms for DCIS patients who received BCS. A large randomized controlled trial would be providing the best evidence to guide treatment recommendations, but the results would not be available for at least 10 years. Our project will use existing data to swiftly provide comprehensive information about comparative effectiveness across the DCIS care continuum in an observational study setting.

Study objectives

Using the Surveillance, Epidemiology, and End Results (SEER)-Medicare linked data, our project's overarching aims are:

Among older women with DCIS who have received BCS as their first surgery, to compare the outcomes of receiving SLNB vs. not receiving SLNB within 6 months of DCIS diagnosis:

Aim 1: We will determine associations between SLNB and acute/subacute side effects, including lymphedema, pain, and limitation of movement of upper extremity from the first BCS to 9 months post-diagnosis.

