Aim 2: We will determine associations between SLNB and long-term outcomes, including breast cancer specific mortality, ipsilateral invasive breast cancer diagnosis, subsequent mastectomy as treated recurrence, and lasting side effects, from >9 months post-diagnosis to death or the end of this study period.

Study design

We will conduct a retrospective cohort study. Using the most up-to-date SEER-Medicare database, we will examine the impact of SLNB on clinical outcomes of women with newly diagnosed DCIS among the Medicare population. The nature of SEER-Medicare linking Medicare claims records to tumor registries participating in the NCI's SEER program allows us to select study population based on precise demographic and clinical characteristics of the patients. In our study, the population is DCIS patients older than 67 years (hereafter referred to as older women) who were enrolled in a fee-for-service Medicare program and resided in the SEER areas from 1998 to 2011 (1998-2013 for Aim 2) and who were followed up to 2012 (2015 for Aim 2).

Methodology

Our study population are generated within the SEER-Medicare linked database. To identify patients with DCIS, we will use histology and behavior codes, which are converted from the ICD-O-3 codes that tumor registries are required to report to SEER for all cases.¹⁶ Specifically, we will identify breast “cancer” patients with in situ tumor behavior (behavior code = 2). DCIS patients will be further limited to those with ICD-O-3 codes consistent with epithelial origin. We select age 67 as a cut-off value because we plan to use two years of claims data to identify patient comorbidities and to control for them in our statistical models, and data is first available at age 65.

Our Aim 1 cohort will include DCIS patients who received BCS as their first surgery (i.e. excluding patients who received mastectomy first). We expect that patients who received BCS with SLNB (compared with those who received BCS without SLNB) would be more likely to end up with mastectomy, and thus would be more likely to have side effects. Findings of the associations between SLNB and mastectomy as the final treatment for DCIS would be informative. We intend to include these patients in Aim 1 so that we can provide a comprehensive picture regarding side effects of SLNB in the context of less intensive managements.

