Our Aim 2 will examine the long-term outcomes between patients who received BCS without SLNB and patients who received BCS with SLNB. Patients who received BCS in the beginning yet ended up with mastectomy for their primary DCIS will be excluded. For patients who received BCS plus RT, SLNB will not likely provide any benefits since RT is able to control small lesions. However, we plan to determine the effects of SLNB among patients who received BCS without RT, which will have important clinical implications.

The time period for defining the cohort for the Aim 1 will be between January 1998 and December 2011. Using medical claims for this cohort, we will identify any side effects within a

9-month window (from DCIS diagnosis to 9 months post-diagnosis). The time period for defining the cohort for the Aim 2 will be from January 1998 to December 2012, and patients will be followed from 9 months after DCIS diagnosis through the latest date to which data is available in SEER-Medicare. For instance, the next SEER-Medicare linked dataset will have overall mortality through December 2015, breast cancer specific mortality through December 2013, and claims data (to identify treated recurrence) through December 2014.

We identify interventions and comparators in our study using specific international classification of Diseases, Ninth Revision, (ICD-9) codes, CPT codes and HCPCS codes. We will limit our sample to DCIS patients who received BCS as their first surgery; that is, we exclude patients whose first surgery is mastectomy, because we are only interested in patients who receive less intensive treatment and their outcomes. Because SLNB is performed by a surgeon, we identify it within a window consistent with those used in prior literature to identify breast cancer surgery, that is, between the date of the first BCS and 6 months after DCIS diagnosis. We are aware that patients may receive BCS first and mastectomy later for their primary DCIS. Furthermore, we realize that SLNB may affect whether or not patients receive mastectomy.

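### Aim 1 counts any lymphedema, pain or limited-movement claim as a side effect and does not deal with prior claims, so pre-existing conditions dilute the SLNB effect and, if unbalanced, bias it in either direction

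*Combined protocol and SAP*

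**What the plan says.** Under Expected outcomes of the study, for Aim 1 "our primary outcome is the side effect occurrence within 9 months post-DCIS-diagnosis". The same section lists the components: "The side effects include lymphedema, pain and limitation of movement of extremities". The Methodology section describes how they are found: "Using medical claims for this cohort, we will identify any side effects within a" nine-month window, which it defines as running "from DCIS diagnosis to 9 months post-diagnosis".

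The Study objectives section differs on two details. It restricts the movement component to the arm and opens the window at surgery: "limitation of movement of upper extremity from the first BCS to 9 months post-diagnosis".

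Pre-diagnosis claims are available. The age cut-off of 67 was chosen because "we plan to use two years of claims data to identify patient comorbidities" and Medicare data begin at 65. The plan also uses prior hospitalization, physician visits and influenza vaccination. None of these uses concerns earlier lymphedema, pain or limited movement.

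**The concern.** The outcome as written is the presence of a claim in a window, not the onset of a condition. Pain and limited movement are non-specific, and a woman over 67 may well have had either before her DCIS was found. If her care continues, she produces a claim in the window and is recorded as having a side effect, whichever group she is in.

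Aim 1 exists to measure the harms of SLNB. Events that SLNB could not have caused make the two groups look more alike. A diluted odds ratio could then be read as evidence that the procedure does little harm. Opening the window at diagnosis adds to the problem, because a claim made between diagnosis and first surgery would count. SLNB itself is identified only from first BCS onward.

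**Working it through.** **What the plan does about prior claims.**

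- Exclusions (Methodology; Data management and statistical analysis): mastectomy as first surgery, and lack of fee-for-service claims from diagnosis to the end of follow-up. There is no exclusion for a prior side-effect claim.
- Matching variables (Data management and statistical analysis): age, race, metropolitan residence, comorbidity, vaccination or primary care visit, income, preoperative MRI and tumor characteristics. No prior side-effect claim is listed.
- Covariates (Methodology): these add, among others, the Elixhauser index, a disability index and prior hospitalization. No prior side-effect claim is listed.
- Aim 1 models: two conditional logistic models, which differ only in whether they adjust for treatment received.

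**Window and limb.** Study objectives opens the window at first BCS; Methodology opens it at diagnosis. Expected outcomes counts nine months from diagnosis, which fits Methodology but is less explicit. Study objectives says upper extremity; Expected outcomes says extremities.

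**Size.** The documents give no event rate, baseline prevalence, sample size or power, so there is no figure to reproduce. Everything below is assumed.

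Let q be the share of a group with a prior condition that produces a claim in the window, and p the new-onset risk among the rest.

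Observed risk = q + (1 − q) × p

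With q equal in both groups, observed risk difference = (1 − q) × (p1 − p0). It shrinks but keeps its sign.

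Assume p1 = 0.15 with SLNB and p0 = 0.10 without. At q = 0.20, for example, the risks are 0.20 + 0.80 × 0.15 = 0.32 and 0.20 + 0.80 × 0.10 = 0.28, and the RR is 0.32 / 0.28 = 1.14.

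| q, both groups | SLNB | No SLNB | Difference | RR | OR |
|---|---|---|---|---|---|
| 0% | 0.150 | 0.100 | 5.0 points | 1.50 | 1.59 |
| 10% | 0.235 | 0.190 | 4.5 points | 1.24 | 1.31 |
| 20% | 0.320 | 0.280 | 4.0 points | 1.14 | 1.21 |
| 30% | 0.405 | 0.370 | 3.5 points | 1.09 | 1.16 |

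For a rarer outcome a smaller q does as much damage. With new-onset risks of 4% and 2% (RR 2.00), q = 5% gives 0.088 / 0.069 = 1.28 and q = 10% gives 0.136 / 0.118 = 1.15.

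**Unequal prevalence**, again with 15% and 10% new onset:

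- q = 15% with SLNB, 20% without: 0.15 + 0.85 × 0.15 = 0.2775 against 0.28, RR 0.99. The harm disappears.
- q = 20% with SLNB, 10% without: 0.32 against 0.10 + 0.90 × 0.10 = 0.19, RR 1.68. This is above the true 1.50.

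**Does exclusion cost too much sample?** Take 502 SLNB women and 1,004 controls. This gives 80% power for 15% against 10% at q = 0, at an assumed two-sided 5% level and ignoring the matching. At q = 10%, 20% and 30%, power is 53%, 36% and 26% with prevalent cases left in. With them removed it is 76%, 71% and 66%, after allowing for the smaller sample.

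**The case against.** The plan is not without protection. It matches on comorbidity and on proxies for access to care, its covariates include a disability index and prior hospitalization, and it adjusts for covariates left unbalanced. A disability index is a plausible proxy for chronic limited movement. This stands in part: these measures may reduce imbalance in prior conditions, and so make the unequal-prevalence examples less likely. They do not touch dilution, which occurs with perfectly balanced groups.

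It can also be said that calling the outcomes acute or subacute side effects implies events after surgery, and that no code list is given. Narrow, procedure-related or arm-specific codes would leave less contamination. That bears on size. It does not supply a new-onset rule, and the text on claims refers to any side effect in the window.

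A reader might infer that prevalent conditions will reverse the SLNB effect, or hide a real harm because healthier women are chosen for SLNB. The documents do not support this. Equal prevalence cannot change the direction. Reversal needs more prior conditions among non-SLNB women after matching, which the documents neither show nor rule out, and a large enough imbalance the other way would exaggerate harm.

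Finally, exclusion drops women whose existing condition SLNB might worsen. Starting at first BCS also still counts claims made before an SLNB done later, since SLNB may occur up to six months after diagnosis. Both are fair limits on the repair, not reasons to leave the outcome as it is.

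**Conclusion.** The point holds. As written, Aim 1 counts prevalent conditions as side effects and, under the Methodology window, claims made before surgery too. Dilution follows arithmetically wherever prevalent cases are present and balanced; bias in either direction follows if they are not.

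The size is unknown. An RR of 1.50 falling to 1.24, 1.14 or 1.09 is an illustration. It assumes the new-onset risks and prior prevalences, and that every woman counted in q has a claim in the window regardless of SLNB. The problem is probably largest for pain and limited movement, the least specific components, but the documents give no figure for any of the three. The differences in window start and limb are separate inconsistencies that add to it. The outcome should be redefined before it is analysed.

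**What to change.** 1. For each side effect separately, exclude women with a claim for that condition in the two-year pre-diagnosis look-back, so that the outcome is incident. Apply this before matching, because removing women afterwards would break matched sets.
2. Require fee-for-service coverage throughout the look-back. The present rule covers only the period from diagnosis onward, and absent claims would otherwise be taken as absence of the condition.
3. Start the window at first BCS throughout, and reconcile Study objectives, Methodology and Expected outcomes on both the start and the limb.
4. Report the prevalence of prior claims by group for each side effect.
5. Keep the all-comers analysis, adjusted for a prior-claim indicator, as a sensitivity analysis.

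The cost is a short programming step on claims the plan already intends to use, and a matched cohort for each side effect. The at-risk group becomes somewhat smaller, and the primary result will apply to women without the prior condition, which the report should say.
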